Supportive Analysis of the primary endpoint - Negative Binomial Regression. A supportive analysis of the primary endpoint Moderate to Severe CIPN (yes/no) at 9 months after first dose of IMP will be analysed by a negative binomial regression model adjusted for study (POLAR-A / POLAR-M) and region (Asia / non-Asia). An offset variable will also be used to adjust for the oxaliplatin exposure defined as the logarithm of the cumulative dose of oxaliplatin received by each patient. Estimate of the treatment contrast (rate ratio) and its corresponding 95% confidence interval will be based on the anti-log of the model parameter estimate and CI.

SAS Code Example Negative Binomial Regression using PROC GENMOD

```
PROC GENMOD;
  CLASS study region trt;
  MODEL cipn = study region trt/DIST=negbin LINK=log SCALE=deviance OFFSET=log_exp;
  ESTIMATE 'PledOx 5 µmol/kg vs Placebo' trt 1 -1;
  LSMEANS trt / CL EXP;
RUN;
```

If convergence criterion is not met using PROC GENMOD an alternative using PROC NLMIXED will be used.

SAS Code Example Negative Binomial Regression using PROC NLMIXED

```
PROC NLMIXED;
  PARMs b0 -2 b1 .1 b2 -.01 b3 .1 phi .1;
  eta = log_exp + b0 + b1*(study=1) + b2*(region=1) + b3*(trt=0);
  mu = exp(eta);
  LL = y*log(phi*mu) - (y+(1/phi))*log(1+(phi*mu)) + lgamma(y+(1/phi)) -
lgamma(1/phi) - lgamma(y+1);
  MODEL y ~ general(LL);
RUN;
```

Exploratory Analysis – Exact Logistic Regression. An exploratory analysis of the primary endpoint Moderate to Severe CIPN at 9 months after first dose of IMP will be analysed by exact logistic regression model adjusted for study (POLAR-A / POLAR-M) and region (Asia / non-Asia). Estimate of the treatment effect and its corresponding 95% confidence interval will be based on the odds-ratio.

SAS Code Example Exact Logistic Regression

```
PROC LOGISTIC DESC;
  CLASS study region trt(ref='0: Placebo');
  MODEL cipn = study region trt;
  EXACT trt;
RUN;
```

Using the same example data presented above, a crude estimate of the odds-ratio then is:

$$(0.27/0.73) / (0.41/0.59) = 0.53$$

Table 4 Example data: Exact Logistic Regression of Moderate to severe CIPN 9 months after first dose of IMP

	N	CIPN (%)	Odds-ratio	95% CI	P-value
PledOx 5 µmol/kg	118	27.1	-	-	-
Placebo	118	40.7	-	-	-
PledOx 5 µmol/kg vs Placebo	236	-	0.54	[0.31;0.94]	0.0293

Data Presentations

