- Table: the primary analysis of Moderate to Severe CIPN based on the Cochran-Mantel-Haenszel estimate will be presented by number of patients (N), treatment estimates and its 95% CIs. The rate ratio between PledOx 5 µmol/kg and Placebo will be presented by the estimate, 95% CI and p-value.
- Table: the supportive analysis of Moderate to Severe CIPN based on the negative binomial regression model will be presented by number of patients (N), treatment estimates and its 95% CIs. The rate ratio between PledOx 5 µmol/kg and Placebo will be presented by the estimate, 95% CI and p-value.
- Table: the number and percentage of patients with Moderate to Severe CIPN along with its 95% CI presented by treatment group and total for each treatment visit/assessment visit. The confidence intervals will be based on the method of Clopper-Pearson (exact).
- Table: the exploratory analysis of Moderate to Severe CIPN based on the exact logistic regression model will be presented by number of patients (N), number of patients (%) with Moderate to Severe CIPN at 9 months after first does of IMP for each treatment group, and odds-ratio, 95% CI and p-value for the treatment comparison.
- Figure: the proportion (including 95% CIs) of patients with Moderate to Severe CIPN will be graphically depicted (lineplot) vs treatment cycle/assessment visit by treatment group.
- All observed values of Moderate to Severe CIPN will be listed by patient.

Missing values of the primary endpoint will be handled as described in Section 5.2.

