5.4.10 Change in Pain (NRS)

The proportion of patients with a 2-point, 3-point and 4-point increase vs baseline in worst pain in hands or feet in the past week using NRS at 9 and 12 months after the first dose of IMP.

Baseline is defined as the time of administration of the first dose of IMP (Day 1, Cycle 1).

Exact Logistic Regression. The proportion of patients with a 2-point, 3-point and 4-point increase from baseline in worst pain in hands or feet will be analysed by an exact logistic regression model adjusted for study (POLAR-A / POLAR-M) and region (Asia / non-Asia). Estimate of the treatment effect and its corresponding 95% confidence interval will be based on the odds-ratio.

Data presentations

- Table: number and percentage of patients having a 2-point, 3-point and 4-point increase in worst pain in hands or feet based on the exact logistic regression model will be presented by number of patients (N), number of patients (%) with 2-point, 3-point and 4-point increase in worst pain in hands or feet at 9 and 12 months after first doses of IMP, respectively for each treatment group, and odds-ratios, 95% CIs and p-values for the treatment comparisons.

All values will also be listed by patient.

The analyses will be based on the observed cases. Hence, no imputation of missing values will be done.

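### Section 5.1.1 plans an odds ratio and 95% CI from exact logistic regression, but the sample code requests only the exact test and the interval in Table 4 is not the standard exact one (minor)

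*SAP*

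**What the plan says.** SAP Section 5.1.1 includes an exploratory exact logistic regression of moderate to severe CIPN at 9 months, adjusted for study and region. It states: "Estimate of the treatment effect and its corresponding 95% confidence interval will be based on the odds-ratio". The list of data presentations at the end of that section promises a table from the exact model with event counts "and odds-ratio, 95% CI and p-value for the treatment comparison".

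The sample SAS code is a PROC LOGISTIC step with three parts:
- a CLASS statement that sets placebo as the reference level and names no parameterisation;
- an ordinary MODEL statement;
- `EXACT trt;` with nothing after it.

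The worked example follows, introduced by "Using the same example data presented above, a crude estimate of the odds-ratio then is". Its result is shown in "Table 4 Example data: Exact Logistic Regression of Moderate to severe CIPN 9 months after first dose of IMP": odds ratio 0.54, 95% CI [0.31;0.94], p = 0.0293.

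Section 5.4.10 names the same method for 2-, 3- and 4-point increases in worst pain at 9 and 12 months, six analyses in all. The outcome "will be analysed by an exact logistic regression model adjusted for study" and region. That section prints no code and no example.

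**The concern.** A reader of the planned table will take the odds ratio, its interval and the p-value as all coming from the exact analysis. The code as written requests only the exact test. The only odds ratio and limits in its output are the default maximum-likelihood ones with Wald limits. The reported table would then pair an exact p-value with an asymptotic interval under one exact label.

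The two can disagree about whether an odds ratio of 1 is excluded. That is most likely when events are few, which is the situation in which an exact method is usually chosen. Table 4 can be checked against this, because the counts behind it are printed in Table 2.

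**Working it through.** **Inputs (SAP Section 5.1.1, Table 2).** PledOx 5 µmol/kg: 32 with CIPN, 86 without. Placebo: 48 with, 70 without. Each arm has 118 patients. The text says Table 4 uses the same data.

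**Step 1. Wald analysis, which reproduces the printed interval.**
- OR = (32 × 70)/(86 × 48) = 2240/4128 = 0.5426
- SE(log OR) = √(1/32 + 1/86 + 1/48 + 1/70) = 0.2793
- 95% CI = exp(−0.6113 ± 1.96 × 0.2793) = 0.314 to 0.938
- Wald p = 0.0286

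Rounded, this is 0.54 [0.31;0.94], the estimate and interval in Table 4. The printed p of 0.0293 differs slightly from the crude 0.0286. Adjustment for study and region could account for that, but the example's strata are not given.

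**Step 2. Exact conditional analysis of the same counts** (both margins fixed, non-central hypergeometric, 2.5% in each tail).
- Conditional estimate 0.544
- 95% CI 0.302 to 0.971, which rounds to [0.30;0.97]
- Two-sided exact p = 0.0388

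The log-scale width is ln(0.9381/0.3139) = 1.095 for Wald and ln(0.9713/0.3018) = 1.169 for exact. The ratio is 0.937, so Wald is about 6% narrower.

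**Step 3. Other candidate intervals.**

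| Method | 95% CI | Rounds to [0.31;0.94]? |
|---|---|---|
| Wald | 0.314 to 0.938 | yes |
| Profile likelihood | 0.312 to 0.934 | no (0.93) |
| Exact conditional | 0.302 to 0.971 | no |
| Mid-p conditional | 0.3125 to 0.9399 | yes (doubled mid-p p = 0.0290) |

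**Step 4. Could the unseen study and region strata explain the printed interval?** The 236 patients were split at random into assumed study and region groups 400 times, and each split was analysed with both factors in the model.
- The exact result never rounded to 0.54 [0.31;0.94].
- The exact interval contained the Wald interval in all 400 splits.
- The narrowest exact log-width was 1.164. The printed limits, allowing for rounding, permit at most ln(0.945/0.305) = 1.131.
- The Wald result matched the printed estimate and interval in 51 splits, 8 of them also with p close to 0.0293. Mid-p matched in 35, 6 of them also in p.

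In a separate set of 1,500 random splits into four assumed strata, 333 gave a conditional odds ratio of 0.535 to 0.545. Their exact upper limit ran from 0.956 to 0.984. The exact stratified p ran from 0.027 to 0.039, so 0.0293 is attainable as an exact p.

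**Step 5. What few events would do.** The SAP gives no event rates for the pain outcomes. The counts below are assumptions, unadjusted, with 118 per arm.

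| Events (active vs placebo) | Wald 95% CI | Exact 95% CI | Exact p | Wald narrower by (log scale) |
|---|---|---|---|---|
| 4 vs 12 | 0.097 to 0.991 | 0.071 to 1.068 | 0.067 | 14% |
| 5 vs 14 | 0.114 to 0.944 | 0.090 to 1.013 | 0.053 | 13% |
| 2 vs 9 | 0.044 to 0.988 | 0.022 to 1.047 | 0.059 | 20% |

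In each row, the code as written would print an exact p above 0.05 beside an interval that excludes 1.

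**The case against.** The strongest reply is that the planned method is right and only an illustrative snippet is incomplete. The block is labelled as example code, the output shells are in a separate document, and the text asks for exact results. A programmer following the text could add the missing option. That is fair, and it rules out saying that the trial's intervals will be asymptotic. The code is still the only specification of how the analysis is run, and the example printed under the exact heading does not carry the standard exact interval.

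Four further inferences are tempting, and the documents do not support them:
- *That Table 4 is proven to be Wald.* Mid-p limits round to the same values. Wald is the likelier source only because the code does not ask for mid-p limits. What `EXACT trt;` prints by default is knowledge of the software and is not stated in the SAP.
- *That p = 0.0293 is wrong.* The unadjusted exact p is 0.0388, but the adjusted one depends on strata that are not given and can reach 0.0293.
- *That [0.30;0.97] belongs in Table 4.* It is unadjusted, while the planned model adjusts for study and region. Inserting it would create a new mismatch.
- *That Section 5.4.10 contains an error.* It names the method and prints no code, so nothing there is wrong. It matters only because the same code would naturally be reused.

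The practical effect is also small. Table 4 is example data, both intervals exclude 1, and the analysis is outside the formal testing procedure in Section 3.

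**Conclusion.** The point holds as a minor error in the plan as written. The text of Section 5.1.1 calls for an exact odds ratio and interval, the sample code does not request them, and the interval in Table 4 is consistent with Wald limits and narrower than the exact one. On the SAP's own counts the upper limit is 0.94 where the unadjusted exact value is 0.97. No conclusion in the example changes.

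This rests on the default behaviour of the EXACT statement in PROC LOGISTIC and on Table 4 using the Table 2 counts, as the SAP says. The adjusted exact interval for the example cannot be computed from the document. The larger gap for rare pain increases rests on assumed event counts. The primary analysis, a Mantel-Haenszel rate ratio, is unaffected.

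**What to change.** In the Section 5.1.1 sample code:
- Add `/ PARAM=REF` to the CLASS statement. Under the default effect coding, the exact parameter for treatment is not the log odds ratio against placebo.
- Replace `EXACT trt;` with `EXACT trt / ESTIMATE=BOTH;`.
- State that the reported odds ratio, 95% CI and p-value all come from that exact output.

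Rerun Table 4 on the example data set with study and region in the model. Do not insert the unadjusted figures given here. In Section 5.4.10, refer to the same code. If asymptotic estimates are intended, rename the method in both sections.

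The cost is two code options, one rerun example table and one cross-reference. The intervals become slightly wider.

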5.2 Handling of Missing Data in the Primary Endpoint

For the primary endpoint Moderate to Severe CIPN (yes/no) the following methods of imputation will be used for the primary analysis in case of missing:

1. Observed cases (no imputation)
2. “Non-responder” if missing (ie 3 or 4 on FACT/GOG)
3. Tipping point analysis – combinations of missing data values that would change the conclusion. References eg Yan (2009), Rubin (2012)

A tipping point analysis assesses the potential impact of informative missingness by progressively penalizing patients with missing data in the experimental arm. The goal is to find the level of penalization that results in loss of statistical significance on the primary endpoint.

The steps to perform the tipping point analysis are as follows:

1. The NB model as described in Section 5.1.1 is applied to each randomised treatment arm separately based on the observed data in that arm. This will give two parameters for each of the experimental and control groups, the event rate, μ , and the dispersion rate, κ .
2. For each subject, i , in the experimental arm who had $t_i < 9$ months follow-up and who did not record a primary endpoint event in the period $(0 - t_i]$, simulate their event rate, μ_i , by randomly sampling an observation from a $Gamma(shape = 1/\kappa, scale = 1/(\kappa\mu))$ distribution.
3. Using μ_i , the time to event for subject i in the period $(t_i, 9]$ is given by $\Delta_i = -\ln(1 - \omega_i)/\mu_i$ where ω_i is a random deviate from a $U(0,1)$ distribution.
4. If $t_i + \Delta_i \leq 9$ then subject i is considered to have had an event at with an exposure time of $t_i + \Delta_i$. If $t_i + \Delta_i > 9$ then subject i is considered not to have event at with an exposure time of 9 months.
5. Steps 2-4 will result in a full dataset with no missing primary endpoint data over the period (0-9] months.

6. This full dataset is then analysed in the same manner as described for the primary endpoint using the Cochran-Mantel-Haenszel approach and the treatment effect and associated SE are estimated.
7. Steps 2-6 are repeated multiple times and the resulting treatment effect estimates and SEs are combined in SAS via PROC MIANALYZE using Rubin's rules. This will provide the estimated treatment effect having imputed missing data under a missing at random assumption.
8. Return to Step 2 and now, for each subject, i , in the experimental arm who had $t_i < 9$ months follow-up and who did not record a primary endpoint event in the period $(0 - t_i]$, resimulate their event rate, μ_i , by randomly sampling an observation from a *Gamma*($shape = 1/\kappa, scale = 1/(\kappa(\mu + \varepsilon))$) distribution where ε is some small, positive number. Imputation of control treated patients is unchanged.
9. Repeat Steps 2-7. This will provide the estimated treatment effect having imputed missing data under a missing not at random with the event rate on experimental penalised by the amount ε .
10. Repeat steps 2-9 for penalising the experimental event rate by $\varepsilon, 2\varepsilon, 3\varepsilon, \dots$ until statistical significance is lost.

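### SAP 5.2 tipping-point analysis: the Gamma scale is inverted, so the penalty works backwards, and a rate per mg/m² is used as a monthly hazard

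*SAP*

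**What the plan says.** Section 5.2 lists three treatments of missing primary-endpoint data: observed cases, missing counted as an event, and a tipping-point analysis in ten steps.

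- **Step 1** fits the negative binomial model of Section 5.1.1 to each arm, giving "two parameters for each of the experimental and control groups": the event rate μ and the dispersion κ.
- **Step 2** samples a patient-level rate from "Gamma(shape = 1/\kappa, scale = 1/(\kappa\mu" (closing brackets omitted), for experimental-arm patients with under 9 months of follow-up and no event so far.
- **Steps 3 and 4** turn that rate into an exponential waiting time on a scale of months. A patient who does not reach the event by month 9 is "considered not to have event at with an exposure time of 9 months".
- **Step 5** states that "Steps 2-4 will result in a full dataset with no missing primary endpoint data over the period (0-9] months".
- **Steps 6 and 7** analyse the completed data with the primary Cochran-Mantel-Haenszel (CMH) method and combine by Rubin's rules. The result is described as "having imputed missing data under a missing at random assumption".
- **Step 8** changes the Gamma to "shape = 1/\kappa, scale = 1/(\kappa(\mu" plus ε (closing brackets omitted) and adds "Imputation of control treated patients is unchanged".
- **Steps 9 and 10** describe this as "missing not at random with the event rate on experimental penalised by the amount" ε, and increase ε until significance is lost.

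**The concern.** A Gamma distribution with shape 1/κ has mean μ only if its scale is κμ. Steps 2 and 8 print the reciprocal of that. A programmer who passes the printed expression as a scale gets a very large sampled rate in the run meant as the missing-at-random anchor. Because μ+ε sits in the denominator, a larger penalty makes the experimental arm look better.

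A second error sits behind the first. The model supplying μ has the log of cumulative oxaliplatin dose as its offset. Section 5.1.1 says its rates are read like the CMH rates, per unit dose. Step 3 then uses μ as a rate per month, with no conversion.

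This is the only graded missing-not-at-random check on the primary endpoint. If it cannot run as intended, a significant primary result has no usable tipping point behind it.

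**Working it through.** **1. The SAP's own figures.** Section 5.1.1, Table 3, gives 0.000317 (PledOx) and 0.000462 (placebo). Times 800 these are 0.254 and 0.370, as printed. With the Table 2 counts (32 and 48 events), exp(ln 0.6869 ± 1.96·√(1/32 + 1/48)) = 0.439 to 1.074, against the printed 0.4391 to 1.0745. So 0.000317 per mg/m² is a fair example of μ. The observed share in that arm is 32/118 = 27%.

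**2. Which Gamma.** The NLMIXED likelihood in Section 5.1.1 is a Poisson mixed over a Gamma with mean μ and variance κμ² (the SAP writes φ for κ). Shape × scale = μ gives scale κμ. As printed, the mean is (1/κ) × 1/(κμ) = 1/(κ²μ), which is 3,155 at κ = 1 instead of 0.000317.

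**3. Imputed event share.** With scale s and L months left, steps 2–4 give P(event) = 1 − (1 + sL)^(−1/κ). For example, at κ = 1 and L = 3: s = 3,154.6 and P = 1 − 1/9,464.7 = 99.99%. The SAP gives no κ, so it is varied. Ranges are for L = 3 to 9.

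| κ | literal, ε = 0 | literal, ε = 10μ | literal, ε = 100,000μ | scale κμ, ε = 0 |
|---|---|---|---|---|
| 0.1 | 100% | 100% | 99.87–100% | 0.10–0.28% |
| 0.5 | 100% | 100% | 29–59% | 0.10–0.28% |
| 1 | 99.99–100% | 99.88–99.96% | 9–22% | 0.10–0.28% |
| 2 | 98.5–99.2% | 95.2–97.2% | 2–6% | 0.10–0.28% |
| 5 | 78–82% | 64–71% | 0.4–1.1% | 0.09–0.28% |

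For every κ the literal share falls, or stays at its ceiling, as ε grows. The inversion does not depend on the unit error: with μ converted to months (0.000317 × 800/9 = 0.0282), the literal 6-month share at κ = 1 is still 99.5%.

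**4. Effect on the conclusion (assumed illustration).** The SAP gives neither a missing-data rate nor the mITT size. Assume 200 per arm, about 27% against 41% events among observed, equal dose of 856 mg/m² (0.2712/0.000317), one stratum, 3 months followed, and controls imputed with control parameters. With equal exposure the CMH ratio is the ratio of events, and the variance of its log is 1/E₁ + 1/E₂. At 5% missing the literal run gives (51+10)/(78+10) = 0.69, SE √(1/61 + 1/88) = 0.167, p = 0.028. The tipping searches used κ 0.05 and 1.

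| Missing per arm | Observed events | Observed-case RR, p | Literal MAR RR, p | Scale-only fix: ε/μ at loss (imputed share) | Scale and units fixed: ε/μ at loss |
|---|---|---|---|---|---|
| 5% | 51/190 v 78/190 | 0.65, 0.018 | 0.69, 0.028 | 270–360 (about 40%) | 3.9–6.6 |
| 10% | 49/180 v 74/180 | 0.66, 0.025 | 0.73, 0.051 | 77–83 (about 14%) | 1.1–1.4 |
| 20% | 43/160 v 66/160 | 0.65, 0.029 | 0.78, 0.095 | 27–28 (about 5%) | 0.5 |

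The literal column equals missing counted as an event in both arms. At 5% missing it never tips; at 10% and 20% significance is already gone at zero penalty.

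**5. Scale corrected, units left.** To bring the imputed share up to the observed 27%, the rate must reach −ln(0.73)/(0.000317 × 6) = 165 times μ with 6 months left, or 110 times with 9. At 10% and 20% missing the search stops at an imputed share below the arm's own observed share, so the size of the penalty has no sensible reading.

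**6. Other loose ends in the steps.**
- Step 4 sets exposure in months, while the CMH divisor is cumulative oxaliplatin dose (Sections 2.5 and 5.1.1).
- Steps 2–4 name only the experimental arm, although steps 1, 5 and 8 presuppose control imputation.
- A first-event time is imputed, although the endpoint is status at month 9.
- No rule covers κ = 0, where 1/κ is undefined. With a 0/1 response and study and region terms (180 per arm, 3–12 cycles), the likelihood score at κ = 0 was positive in none of 500 simulated arms in each of three dose–risk patterns. That checks the likelihood only, not PROC GENMOD with the deviance scaling the SAP specifies.

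**The case against.** The strongest reply is that this is a mislabel. The printed expression is the correct inverse scale, and an experienced programmer might enter it as such or notice an anchor that imputes nearly everyone as an event. That is plausible, but a SAP should not rely on silent correction, and the unit error would remain.

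Second, a binary response probably drives κ to zero, where the literal rule cannot run at all. Near zero the reversed ε does almost nothing: at κ = 0.1 the imputed share is still at least 99.8% at ε = 100,000μ. This stands. The visible drift toward PledOx needs a larger κ together with a very large ε; for small κ the right description is that the penalty has no useful effect. Conversely, at κ = 5 the imputed share already moves materially by 10μ. None of these cases lets the search work.

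Third, the illustration rests on assumptions and is fragile at 10% missing: p = 0.051, and one fewer experimental event gives 0.042. With 240 per arm the literal p-values are 0.021, 0.027 and 0.074; with 180 they are 0.039, 0.070 and 0.126. This also stands: only the algebra is certain.

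Fourth, step 6 points to dose as the divisor, and steps 1, 5 and 8 show that controls are meant to be imputed. Those two gaps are therefore drafting matters. Finally, the observed-case and missing-as-event analyses are specified separately and are unaffected.

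**Conclusion.** The concern holds and should be fixed. For every positive κ and μ, the printed scale is the reciprocal of the one that the SAP's own likelihood implies, and ε acts in the wrong direction. For κ up to 1 the nominal missing-at-random run imputes at least 99.98% events at the example rate with 3–9 months left; the share weakens to 78–82% at κ = 5. Correcting the scale alone moves the anchor to about 0.1–0.3% against 27% observed, because a per-dose rate is read as a monthly one. With both corrected, the search works in the illustration.

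The algebra and the unit mismatch follow from the SAP alone. The p-values and tipping points rest on the assumed sample size, missing rate, follow-up and κ. The damage is confined to this one sensitivity analysis.

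**What to change.** Make the change before the SAP is finalised and the blind broken, as Section 1 allows.

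**Minimum repair**, a few lines of text and code:
- set the scale to κμ in step 2 and κ(μ+ε) in step 8, or relabel the printed expressions as rate parameters;
- put hazard and exposure on one scale that matches the CMH divisor;
- write out the control-arm imputation with the control parameters;
- give a rule for κ = 0;
- impute status at month 9, not a first-event time.

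**Preferred**, a short rewrite of the subsection: replace steps 1–4 and 8 with binary multiple imputation of month-9 status in both arms. Draw each missing patient's probability from its posterior by arm with study and region, draw the status, and keep the patient's actual cumulative oxaliplatin dose as exposure. Shift the experimental-arm probability or log-odds upward in fixed steps with controls unchanged. Analyse by the primary CMH method and combine log rate ratios by Rubin's rules, stopping when significance is lost or all missing experimental values are events. In the illustration this tips at a shift of +0.47, +0.18 and +0.09 in probability at 5%, 10% and 20% missing. Report the observed-case p beside it: with the SAP's Poisson-type variance, the imputed variance at 20% missing is slightly smaller (0.0358 against 0.0384; p = 0.023 against 0.029).

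The preferred version is a choice; the minimum repair is enough to cure the error. Neither needs new data or adds patient burden.

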The POLAR studies were designed based on the following sample size assumptions:

- POLAR-A: With 112 patients per group, the POLAR-A study has 91% power to detect a reduction (improvement) from 40% to 20% (OR = 0.375) in the primary endpoint using two-sided test controlled at the 0.05 type-I error rate. To account for 20% dropout in the study, in total 280 patients (140 patients per arm) will be randomised.
- POLAR-M: With 112 patients per group, the POLAR-M study has 91% power to detect a reduction (improvement) from 40% to 20% (odds ratio = 0.375) in the primary endpoint using two-sided test controlled at the 0.05 type-I error rate. To account for 20% dropout in the study, in total 420 patients (140 patients per arm) will be randomised.

Table 1: Patient disposition in the POLAR studies

	POLAR-A	POLAR-M	Total
Number of patients randomised	301	290	591
Number of patients dosed with ≥ 1 cycle of IMP	297	285	582
Number of patients dosed with ≥ 6 cycles of IMP	257	194	451
Number of patients dosed with ≥ 12 cycles of IMP	107	98	205

A total of 591 patients was randomised in the POLAR program and 582 patients dosed, of which 451 patients completed 6 cycles and 205 patients completed 12 cycles (see Table 1).

There are two main contributing factors to take into account when designing a reasonable statistical approach to the analysis of the POLAR studies:

- 1) POLAR-M only randomised 290 out of the planned 420 patients. This, together with the reduced dosing of patients (see bullet 2 below) means a separate primary analysis based on this data set cannot be supported.
- 2) Due to the Sponsor's decision to place the dosing of patients on hold on March 1, 2020, not all patients have had sufficient dosing of IMP to expect the full treatment effect of active treatment as assumed in the sample size calculation.

Taking these two aspects into consideration account (the fewer number of randomised patients and the reduced dosing of patients) a reasonable statistical approach is to conduct a combined primary analysis across the two studies, with the data from the two studies regarded as strata, based on a modified ITT analysis set defined by the eligibility of dosing with IMP as intended in the clinical study protocol. In addition, a standalone analysis of the primary endpoint in the fully recruited POLAR-A study will be conducted if the combined analysis is statistically significant. This approach will be further detailed in this document.

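### Followed literally, the tipping-point steps impute only PledOx dropouts, which contradicts the plan's own claim of a complete dataset and a missing-at-random starting point

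*SAP*

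**What the plan says.** SAP section 5.2 lists three ways of handling a missing primary endpoint: observed cases, counting missing as an event, and a tipping-point analysis. The tipping-point steps run as follows.

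- **Step 1** fits the negative binomial model in each arm: "This will give two parameters for each of the experimental and control groups", namely an event rate mu and a dispersion kappa.
- **Step 2** draws an individual event rate for subjects "in the experimental arm who had" under 9 months of follow-up and no event so far. Steps 3 and 4 turn that draw into an event or non-event for the same subjects.
- **Step 5** states the result: "Steps 2-4 will result in a full dataset with no missing primary endpoint data over the period (0-9] months".
- **Step 6**: "This full dataset is then analysed in the same manner as described for the primary endpoint using the Cochran-Mantel-Haenszel approach".
- **Step 7** pools the repeats by Rubin's rules: "This will provide the estimated treatment effect having imputed missing data under a missing at random assumption".
- **Step 8** repeats the draw with epsilon added to the experimental rate and notes: "Imputation of control treated patients is unchanged". Steps 9 and 10 raise epsilon until significance is lost.

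**The concern.** A tipping point can be interpreted only if epsilon = 0 is a like-for-like comparison. The reader then learns how much worse the unseen PledOx outcomes would have to be before the conclusion changes. If PledOx dropouts receive simulated outcomes while placebo dropouts stay missing, the starting ratio already contains a difference in handling, and so does each penalised ratio after it. The epsilon at which significance is lost then no longer measures robustness to missing data alone.

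Two programmers could also work from this text and reach different tipping points, one imputing placebo and one not. A choice between them made after unblinding would be post hoc.

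**Working it through.** **1. The steps side by side**

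| Step | Experimental arm | Control arm |
|---|---|---|
| 1 | mu, kappa estimated | mu, kappa estimated |
| 2–4 | outcomes simulated | nothing specified |
| 5 | said to be complete | said to be complete |
| 7 | called missing at random | called missing at random |
| 8 | redrawn with epsilon | imputation said to be unchanged |

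Steps 2–4 cannot deliver step 5 unless placebo has no missing data. Step 8 leaves unchanged something that was never defined. The other two missing-data methods in section 5.2 are separate analyses and do not fill the gap.

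**2. The plan's own figures**

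The SAP gives no number for the tipping-point analysis. Its Table 3 example can be used to check the variance form. With 32 and 48 events, SE = √(1/32 + 1/48) = 0.228. Around the stated ratio 0.6869 this gives a 95% CI of 0.439 to 1.074 and p = 0.0998. The SAP states 0.4391 to 1.0745 and 0.0999. So SE = √(1/E1 + 1/E0) is adequate for an illustration.

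**3. Assumed inputs (not in the SAP)**

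- 200 patients per arm. 15% (30 per arm) leave at month 6, so 170 per arm are observed at month 9.
- Month-9 rates of 27% for PledOx (Table 2 example) and 40% for placebo (planning value).
- A constant monthly hazard h = −ln(1 − p)/9 in place of the step 2 Gamma draw. The Gamma scale and the unit of mu are separate matters, set aside here.
- Patient counts as denominators, where the plan uses cumulative oxaliplatin. The between-imputation variance is left out.

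The risk over the remaining 3 months for an event-free dropout is q = 1 − (1 − p)^(1/3):
- PledOx: 1 − 0.73^(1/3) = 10.0%
- Placebo: 1 − 0.60^(1/3) = 15.7%

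**4. Observed cases**

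Events are 0.27 × 170 = 45.9 and 0.40 × 170 = 68. R = 0.675, p = 0.040.

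**5. Scenario (a): no dropout had an earlier score of 3 or 4**

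- PledOx completed: 45.9 + 30 × 0.0996 = 48.9 of 200 = 0.244.
- Literal steps, placebo 68/170 = 0.400: R = 0.61, p = 0.009.
- Both arms imputed, placebo 68 + 30 × 0.1566 = 72.7 of 200 = 0.363: R = 0.67, p = 0.032.
- Shift: 0.611/0.672 − 1 = −9%.

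**6. Scenario (b): 30% of PledOx and 45% of placebo dropouts had an earlier score of 3 or 4, counted as events in both arms**

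- PledOx completed: 45.9 + 30 × (0.30 + 0.70 × 0.0996) = 57.0 of 200 = 0.285.
- Literal steps, with only event-free placebo dropouts left missing: events 68 + 13.5 = 81.5, patients 170 + 13.5 = 183.5, rate 0.444. R = 0.64, p = 0.010.
- Both arms imputed, placebo 68 + 30 × (0.45 + 0.55 × 0.1566) = 84.1 of 200 = 0.420: R = 0.68, p = 0.023.
- Shift: 0.642/0.678 − 1 = −5%.

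**7. Side point: fixed parameters**

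Mu and kappa are estimated once and reused in every imputation. For a simple proportion with missing share f and many imputations, the pooled variance is (1 + f)σ²/n, where it should be σ²/[n(1 − f)]. The ratio of the two is 1 − f². The SE is therefore too small by 1 − √(1 − 0.15²) = 1% at f = 0.15 and by 1 − √(1 − 0.30²) = 5% at f = 0.30.

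**The case against.** **Intent can be recovered from the text.** The control parameters from step 1 have no use unless control patients are imputed, and step 8 takes that imputation as existing. Step 2 may simply have lost a few words. This stands as a limit: the unequal comparison is what the text produces, not necessarily what would be programmed. The introductory phrase "progressively penalizing patients with missing data in the experimental arm" does not settle the matter, because it describes the penalty and not the unpenalised start.

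**The reach is limited.** This is the third missing-data method. The observed-case analysis and the missing-as-event analysis treat the arms alike and are unaffected. The primary estimate, test and alpha do not change. This stands too, and it keeps the point below the level of a must-fix.

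**A stronger reading is tempting.** A reader might infer that the literal steps can raise the ratio and lose significance before any penalty is applied. In scenario (b) that result (R = 0.71, p = 0.059, a shift of +5%) appears only if PledOx dropouts with an earlier score of 3 or 4 count as events while placebo dropouts with the same history are left out altogether. Section 5.2 states no such difference between the arms: it simulates event-free subjects and gives no arm-specific rule for the others. A simulation that gave starting ratios of 1.04 to 1.22 under a true ratio of 1 used the same unequal treatment, so it does not support the claim either.

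**There may be no bias at all.** If dropout is unrelated to earlier events and every placebo dropout is left out, simulation at 20% missing gave a mean ratio of 1.00 both ways, and only the SE differed (0.197 literal, 0.185 with both arms imputed). This stands as one possible case.

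**Conclusion.** The contradiction is in the current text and nothing else in the SAP resolves it. If the steps are followed literally, the start labelled missing at random is not a like-for-like comparison, and the tipping point mixes the penalty with unequal handling of the arms.

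With earlier events treated alike in both arms, the literal steps lower R by about 5% to 9% in the two scenarios, which favours PledOx at the start. All p-values in those scenarios stay below 0.05 (0.009 and 0.010 literal; 0.032 and 0.023 with both arms imputed), so no crossing of 0.05 is shown. These figures rest on an assumed missing share, dropout time, early-event shares and arm size. Both size and direction depend on missingness that the SAP does not give. The fixed-parameter point is minor.

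Severity: should be fixed before unblinding.

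**What to change.** In section 5.2:

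1. In steps 2–4, impute every event-free subject with under 9 months of follow-up in either arm, using that arm's own mu and kappa from step 1.
2. State one rule for dropouts who already had an event, and apply it identically in both arms.
3. In steps 8–10, add epsilon to the PledOx arm only and keep placebo at epsilon = 0. Step 8's remark on control patients then refers to something defined.
4. As a minor refinement, redraw mu and kappa from their estimated sampling distribution for each imputation.

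The cost is a few words in the SAP and a small programming change. No new data are needed. The SAP is to be finalised before the blind is broken, so the change can be made then.
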